**The prevalence of local IgE elevation and its effect on intranasal capsaicin therapy
in the non-allergic rhinitis population**

NCT 05093478

Version Date: 05/25/2022

Protocol Title: The prevalence of local IgE elevation and its effect on intranasal capsaicin therapy in the non-allergic rhinitis population

Principal Investigator: [name]

Faculty Investigator: [name], PhD

Study Coordinator: [name]

Population: Non-smoking Adults > 18 years of age with chronic rhinitis

Number of Sites: Single site

Study Duration: 1 year

Subject Duration: 15 weeks

General Information

Our study aims to determine the therapeutic response of patients with non-allergic rhinitis with local IgE elevation to intranasal capsaicin, the prevalence of non-allergic rhinitis with local IgE elevation in the non-allergic rhinitis population, and to determine the change in intranasal IgE after capsaicin treatment.

Background Information

Rhinitis is inflammation of the nasal lining characterized by 2 or more of the following nasal symptoms: congestion, rhinorrhea, sneezing or itching. Chronic rhinitis is categorized as allergic or non-allergic rhinitis. Allergic rhinitis is driven by an IgE-mediated response to allergens in the environment. Non-allergic rhinitis represents a heterogenous group of disorders whose underlying pathology is not IgE-mediated. Allergy testing distinguishes between allergic and non-allergic rhinitis. Subtypes of non-allergic rhinitis include drug-induced, hormonal, atrophic, gustatory, non-allergic rhinitis with eosinophilia syndrome (NARES), and non-allergic rhinitis with local IgE elevation. This heterogenous group can be divided into conditions that demonstrate nasal inflammation histologically (NARES and non-allergic rhinitis with local IgE elevation) and those that do not. Those that do not are often referred to as non-allergic rhinopathy rather than rhinitis due to the lack of inflammation. Allergic rhinitis is typically best treated with a combination of nasal steroids, nasal antihistamines, oral steroids, and oral antihistamines. Non-allergic rhinitis demonstrating inflammation (NARES and non-allergic rhinitis with local IgE elevation) may best be treated similarly. However, non-allergic rhinopathy tends to be driven by an imbalance in autonomic input. Therefore, ipratropium sprays are currently the mainstay of medical therapy for non-allergic rhinopathy. When medical therapy is insufficient, interventions focusing on the ablation of the parasympathetic innervations of the nasal mucosa are options including vidian neurectomy or cryotherapy of the nerve.

A thorough history and physical can sometimes identify a specific subtype of non-allergic rhinitis to guide therapy. However, certain conditions, such as non-allergic rhinitis with local IgE elevation, cannot be confirmed without further evaluation. Two techniques have recently been proposed to differentiate inflammatory and non-inflammatory subtypes of non-allergic rhinitis: detection of local IgE levels from

mucosal brush biopsy of inferior turbinate and optical rhinometry after intranasal capsaicin challenge. These techniques potentially can be combined to subtype non-allergic rhinitis patients and monitor response to treatment.

Mucosal brush biopsy of the inferior turbinate has been demonstrated to be capable of detecting antigen-specific IgE within the nasal mucosa.¹ In fact, Reisacher et al. in 2014 reported that in a group of 20 patients with chronic, idiopathic, nonallergic rhinitis all were found to have antigen-specific IgE to at least 1 antigen.² Other studies have demonstrated that patients with elevated local IgE levels may respond similarly to oral antihistamines and topical nasal steroids as patients with allergic rhinitis. It is this rationale that has led some to propose using nasal provocation testing and local IgE levels in the diagnostic evaluation of patients with non-allergic rhinitis.³

Optical rhinometry is a technique which measures the blood flow in nasal vessels reported as optical density (OD). When used with intranasal provocation testing, it is useful in measuring changes in blood flow which correlates with onset of symptoms and increase in nasal mucosal swelling.⁴ Additionally, the use of optical rhinometry with intranasal capsaicin challenge has been reported as a viable option in the diagnosis of non-allergic irritant rhinitis.⁵

More recently, intranasal capsaicin has been described as a novel therapeutic option for non-allergic rhinitis⁶, and the cellular mechanism underlying its use has been further defined. It has been shown that patients with idiopathic rhinitis have higher baseline levels of transient receptor potential vanilloid 1 (TRPV1) within the nasal mucosa⁷ and lower thresholds for response to TRPV1 agonists.⁸ Treatment with repeated intranasal capsaicin is thought to cause down regulation or degeneration of nerve terminals expressing TRPV1 resulting in a reduction in TRPV1 levels as well as an increase in response threshold to TRPV1 agonists.⁸ This translates into a reduction in nasal symptomology that is sustained through 12 weeks post-treatment.⁷

Our current understanding of outcomes after treatment with intranasal capsaicin is incomplete. Most studies analyzing the effect of intranasal capsaicin have evaluated a heterogeneous group of non-allergic rhinitis patients with idiopathic rhinitis without distinguishing among subtypes. Consequently, we do not know whether certain subtypes of idiopathic rhinitis are more likely to respond to treatment with intranasal capsaicin treatment than other subtypes. Due to the relative paucity of information regarding therapeutic efficacy of intranasal capsaicin for non-allergic rhinitis, the most recent Cochrane review describes capsaicin as an option for patients with idiopathic, non-allergic rhinitis.⁹ We hope to further delineate the group of idiopathic non-allergic rhinitis patients that will benefit from intranasal capsaicin in an effort to refine the treatment algorithm for non-allergic rhinitis.

Objectives

- Primary: To determine the therapeutic response of non-allergic rhinitis patients that have been subtyped as non-allergic rhinitis with local IgE elevation or non-allergic rhinopathy to intranasal capsaicin based on visual analog scale and optical rhinometry
 - The total as well as individual symptom VAS scores at enrollment, 4 weeks post-treatment, and 12 weeks post-treatment will be compared
 - The maximum optical density determined via optical rhinometry at enrollment and 12 weeks post-treatment will be compared
- Secondary: To determine the prevalence of non-allergic rhinitis with local IgE elevation in this study's cohort of patients with non-allergic rhinitis identified by rhinitis history and negative skin

testing for allergic rhinitis, and to determine the change, if any, in intranasal IgE levels after capsaicin treatment.

- The local IgE level obtained from the brush biopsy of the inferior turbinates at enrollment and at 12 weeks post-treatment will be compared

Study Design

- Prospective cohort study
- The study is expected to last 1 year with subject participation lasting 15 weeks.
- Therapeutic response to intranasal capsaicin will be measured using major nasal symptoms on a visual analog scale, as well as optical rhinometry.
 - Nasal symptoms of rhinorrhea, nasal obstruction, nasal itching, and sneezing, will be measured using a visual analog score. Results range from 0-10. The major nasal symptom will be defined as the nasal symptom with the highest score on VAS at screening. The pre- and post-treatment data can be compared to measure change in symptoms.
 - Optical rhinometry: Maximum optical density will be recorded following the initial capsaicin challenge, as well as at 12 weeks post-treatment
- Assessment of efficacy will be based on repeat symptoms scores (nasal symptom inventory pre-treatment and at 4 and 12 weeks, optical rhinometry pre-treatment and 12 weeks post-treatment). Additionally, brush biopsy of the inferior turbinates will be performed pre-treatment and 12 weeks post-treatment in order to determine any change in local IgE levels.
- This study is using previously described methods with good safety profiles. Patients may experience minimal pain and some discomfort with the skin prick test for allergy testing, the mucosal swab for IgE levels, and the intranasal capsaicin.
- Patients will receive skin allergy testing with results and clinic visits with physician at no charge. In addition, study drugs will be provided at no cost to the patient. Although no monetary compensation will be provided for participating in the study, study participants will be reimbursed the fee for parking at all three visits.

Study Population

All patients that present with chronic rhinitis not otherwise classified as allergic based on prior positive skin or blood test to the Texas Sinus Institute will be screened for study inclusion.

Inclusion Criteria:

1. Adult > 18 years of age
2. Chronic rhinitis

Exclusion Criteria:

1. Active smoker
2. Anatomic source of nasal symptoms
3. Chronic rhinosinusitis or other nasal infection
4. History of sinonasal malignancy
5. Pregnancy or lactation
6. Use of medication affecting nasal function (topical steroids, topical anticholinergics, oral antihistamines) in the previous 4 weeks
7. Use or abuse of nasal decongestants.
8. Positive skin prick test for allergic rhinitis

Study Procedures

At the first visit after enrollment:

- Rate major nasal symptoms (rhinorrhea, nasal obstruction, nasal itching, and sneezing) on a visual analog scale
- Complete skin prick allergy testing
- A nasal brushing to determine local IgE levels
- Optical rhinometry with intranasal capsaicin challenge to confirm diagnosis of non-allergic irritant rhinitis¹

This will be followed by treatment:

- Intranasal capsaicin, 5 applications each delivering 2 micrograms in each nostril, separated by 1 hour.
 - The first treatment will be administered in the clinic to demonstrate how the spray is done, and to monitor for any side effects.
 - The patient will then be provided with 4 additional prefilled syringes with capsaicin to be administered at home.
 - The patient will also be provided with a document that will tell them at what time to administer the medication, and so that they can keep track of how many sprays have been completed.

At week 4 post-treatment (+/- 1 week)

- Rate major nasal symptoms on a visual analog scale
- To reduce visits during the study, the VAS at 4 weeks post-treatment can be done remotely. It will be conducted via phone call, email, or mail according to patient preference.

At week 12 post-treatment (+/- 2 weeks)

- Rate major nasal symptoms on a visual analog scale
- A nasal brushing will be obtained to determine local IgE levels
- Optical rhinometry with intranasal capsaicin challenge¹

Information gathered for the study will include: personal health information, major nasal symptoms, allergy skin test results, mucosal IgE levels, and optical rhinometry.

- Any physical information (Consent, VAS, etc.) will be stored in a locked filing cabinet within the locked otolaryngology clinic located at [name]. The data gathered will be entered into a password protected excel spreadsheet and saved on a UT issued passwordprotected laptop.

Allergy skin prick testing

- All consented subjects with history consistent with chronic rhinitis will be screened with a skin prick test (Multi-Test II Lincoln Diagnostics, Decatur, IL USA) to common allergens including dust mite, cat hair, grass pollen, insect extracts, fungi/mold extracts, and bermuda grass extract to exclude allergic rhinitis. Those with confirmed negative skin prick testing (ruling out allergic rhinitis) will be eligible for the study.
 - Having a positive reaction to at least one antigen and the positive control will be considered positive testing, and that subject will be excluded from the study

- Having no reaction to all tested antigens except the positive control will be considered negative testing and that subject will be eligible for the study.

Mucosal brush biopsies

- The mucosal local IgE levels will be obtained according to the protocol demonstrated by Reisacher et al.²
 - A cytology brush will be used to brush the inferior turbinates (3 spins of the brush against the medial aspect of the inferior turbinates). The brush is then washed in saline and stored at -20C.
 - Antigen specific IgE will be determined using reference lab from the processed sample.

Intranasal capsaicin treatment

- The intranasal capsaicin treatment will be completed according to the protocol for treatment of non-allergic irritant rhinitis with intranasal capsaicin established by Van Gerven et al.³
 - Patients will be treated with 5 intranasal doses of capsaicin separated by 1 hour
 - Capsaicin solution (Sigma Chemical, St. Louis, MO USA) will be diluted in 1% ethanol and 0.9% normal saline. A mucosal atomizer device (MAdomizer, Wolfe Tory Medical, Inc, Salt Lake City, UT USA) delivering 100 µL solution will be used to deliver a total dose of 2 µg of capsaicin to each nasal cavity for each application. Each application of capsaicin will be preceded by application of 100 µL of aerosolized 1% lidocaine for anesthesia 15 minutes prior to each planned intranasal capsaicin application.

Data and Safety Monitoring

- Serious adverse events are not anticipated. Patients may experience minimal pain and some discomfort with the skin prick for allergy testing, the mucosal brushing for IgE levels, and the intranasal capsaicin.
- The principal investigator will be notified of any adverse events, protocol deviations, and other problems. These will be addressed immediately by the PI or co-investigators.
- On the first of each month, the PI will review the study to ensure that any events or deviations were reported, to ensure that the study is proceeding strictly according to protocol. The status of the study will be reviewed during a monthly meeting with the rhinologic team which consists of Drs. [name], [name] and [name].

Statistics

In considering our sample size calculation, we considered our primary outcome as the change in VAS for the major nasal symptom. Using the study by Gerven et al. to guide a sample size calculation, we assumed a success rate of capsaicin to be 75% with success defined as a decrease of at least 30% on the VAS for the major nasal symptom. In their study, they enrolled 33 patients with non-allergic rhinitis and showed a significant response to intranasal capsaicin treatment via VAS. Consequently, we will plan for 33 patients with non-allergic rhinitis to complete this study.

Differences between all continuous descriptive factors and both pretreatment and posttreatment outcome measure scores, between participants with and without local IgE elevation, will be evaluated using Mann Whitney U or chi-square (χ^2) testing where appropriate. Significant improvements in outcome measure scores over time and between pretreatment and posttreatment scores will be evaluated using Wilcoxon signed rank tests. Significant differences will be identified at a conventional 0.050 alpha level.

Ethics

- IRB approval will be sought from CPHS
- Prior to obtaining consent, the study and the subject's participation requirements will be fully explained to the subject. They will be given ample time to read the consent, as well as to ask questions. If needed, a copy of the consent can be provided to take home if additional time is needed to review. Consent will then be obtained after the subject has had adequate time to assess the study.

Data handling and record keeping

- Access to source documents will be limited to study personnel with appropriate training.
- Source documents will be de-identified appropriately. Subjects will be assigned a subject number which will be associated with all data gathered from that subject.
- Subjects will be identifiable through their subject number via an excel spreadsheet which links PHI with subject number. The ability to identify subjects via their subject number will only be available to study personnel with appropriate training.
- All data stored in a password protected excel document will be saved on a UT issued password protected laptop.
- All source documents will be stored in a secured filing cabinet within the locked otolaryngology clinic located at [name].

Quality control and assurance

- Printed protocol will be available during data collection to ensure that all steps are followed consistently
- Personnel will be available to answer questions regarding questionnaire completion to ensure that all questions are answered and answered appropriately
- Source documents will be saved to confirm integrity of the data transferred to excel documents for analysis.

Publication Plan

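### If the VAS reading that picks the worst of four symptoms is also that symptom's baseline, its uncontrolled pre/post test is biased towards improvement

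*Combined protocol and SAP*

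**What the plan says.** Study Design has four nasal symptoms rated from 0 to 10 and then fixes one per patient: "The major nasal symptom will be defined as the nasal symptom with the highest score on VAS at screening". Under Statistics, the sample-size paragraph says "we considered our primary outcome as the change in VAS for the major nasal symptom", and adds "we assumed a success rate of capsaicin to be 75% with success defined as a decrease of at least 30% on the VAS" for that symptom. The second paragraph of Statistics compares scores before and after treatment by Wilcoxon signed-rank test at the 0.05 level. The design is a single cohort in which every participant receives capsaicin.

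The Objectives describe the VAS comparison differently: "The total as well as individual symptom VAS scores at enrollment, 4 weeks post-treatment, and 12 weeks post-treatment will be compared". Maximum optical density is the other primary measure.

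The pre-treatment reading goes by several names. It is taken at enrolment in the Objectives, before treatment in Study Design ("nasal symptom inventory pre-treatment and at 4 and 12 weeks"), and at the first visit following enrolment in Study Procedures. No sentence says whether the reading called screening is the same one.

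**The concern.** Each rating is the symptom's usual level plus occasion-to-occasion noise. Choosing the highest of four ratings favours symptoms whose noise happened to be upward that day. If that rating is then used as the baseline, the next one is expected to be lower even when nothing has changed. This is regression to the mean produced by the selection rule.

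A control arm would show the same drift and allow it to be subtracted, but this design has none. The signed-rank test therefore credits the drift to capsaicin. At stake is the major-symptom pre/post result, the outcome on which the plan bases its sample size. If the true effect is small or absent, the test can reject too often.

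**Working it through.** **Step 1: is it one reading?**

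- *For one reading.* Study Procedures list a single pre-treatment VAS, at the first visit. The skin prick test that screens consented subjects is done at that same visit. Study Design says "study participants will be reimbursed the fee for parking at all three visits", and three visits fit first visit, week 4 and week 12.
- *For an earlier reading.* Study Population says that presenting patients "will be screened for study inclusion", while the listed VAS comes after enrolment. Week 4 may be done remotely, so a third visit could be a separate screening visit. Study Design also says "The study is expected to last 1 year with subject participation lasting 15 weeks", whereas the latest follow-up is 12 + 2 = 14 weeks, which leaves one week spare.

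One reading is the more natural inference, but it is not established.

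**Step 2: inputs.** From the documents: four symptoms, a 0-10 scale, 33 patients, signed-rank test, alpha 0.05 (sidedness not stated; two-sided used). The documents give no VAS SD, reliability or symptom profile, and no figure for this effect that could be reproduced. Assumed: between-patient SD 1.5; between-symptom SD within patient τ = 1; occasion error SD σ = 0.5 to 1.5; errors across the four symptoms either independent or half shared; no treatment effect.

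**Step 3: size by formula.** The mean of the largest of four independent standard normals is 1.03. If a patient's four true levels are equal and errors are independent, the expected fall is 1.03σ, which is the ceiling. If the four symptoms have equal population means but vary within patients with SD τ, then

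expected fall = 1.03 × σ² / √(τ² + σ²)

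- σ = 0.5: 1.03 × 0.25 / √1.25 = 0.23 points
- σ = 1.0: 1.03 × 1 / √2 = 0.73 points
- σ = 1.5: 1.03 × 2.25 / √3.25 = 1.29 points

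If half the error variance is shared by the four symptoms, only the unshared half affects which is highest, so σ²/2 replaces σ²: 0.12 points at σ = 0.5 and 0.79 at σ = 1.5.

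**Step 4: simulation.** 1,000 trials of 33 per setting, scores clipped to 0-10, no true effect. Ranges run over σ = 0.5 to 1.5; rejection is two-sided at 0.05.

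| Symptom means | Independent errors: fall; rejection | Half-shared errors: fall; rejection |
|---|---|---|
| 5, 5, 5, 5 | 0.22-1.26; 45-95% | 0.12-0.79; 16-57% |
| 6, 6, 3, 3 | 0.14-0.90; 20-72% | 0.07-0.50; 9-28% |
| 7, 4, 4, 4 | 0.05-0.75; 7-55% | 0.02-0.34; 6-15% |
| 7, 3, 3, 3 | 0.02-0.49; 5-27% | 0.00-0.17; 5-7% |

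The first row agrees with the formula; clipping explains the small shortfall at σ = 1.5. Repeat runs agree within simulation error. The noisiest cell of the last row (independent errors, σ = 1.5) varied between 21% and 27%.

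**Step 5: unselected comparators.** When the symptom is chosen on a separate reading, the mean fall is about 0 and rejection is close to the nominal 5% (4-6%). The same rejection rate holds for total VAS.

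**Step 6: the 30% cut.** With no effect, mean 5, between-symptom SD 2 and σ = 1, 11% of patients meet the 30% cut when one reading does both jobs, against 7% with a separate baseline. The direction is clear, but the size again depends on assumed variances.

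**The case against.** The strongest reply is that the premise cannot be proved. The plan lists a study schematic, a Study Schedule and the VAS form as attachments; none is available here, and a schedule is where a screening VAS would appear. That stands, and it is why the point is conditional. It does not remove the gap in the text, which describes one pre-treatment VAS and uses an undefined word for the selecting one.

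A second reply is that little of the plan is affected. The Objectives name total VAS, individual-symptom VAS and optical density, none of them selected on its own value. The major symptom is called primary only in the sample-size paragraph. This also stands. A reader might infer that the whole primary objective, or the comparison by local IgE status, is biased; the documents do not support that. The first rests largely on unselected measures, and no claim is made about the second.

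A third reply concerns the 75% success rate. A reader might infer that the trial's success rate will be overstated by a definite amount. The 30% criterion appears only as a sample-size assumption, and Statistics commits to no responder analysis. The 75% comes from a cited study whose selection rule is not in the documents, so it may already contain the same effect. Any responder rate that is reported would lean upward, but the amount cannot be calibrated to 75%.

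Finally, the 5-95% range is wide because every variance is assumed. That limits what can be said about size. It does not change the direction.

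**Conclusion.** The concern holds conditionally. On the available text, one reading most plausibly both selects the major symptom and serves as its baseline. If so, the signed-rank pre/post test of that symptom is biased towards improvement, and nothing in the design or analysis removes the bias.

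With no true effect and n = 33, the apparent fall is about 0 to 1.3 points. False rejection is close to nominal when one symptom clearly dominates and the noise is small or partly shared, and about 95% when the four symptoms are equal, errors are independent and the error SD is 1.5. These figures rest on the assumed variances above, not on trial data. If the attachments show a separate earlier screening VAS with a later baseline, this source of bias disappears. Confidence is medium: high for the mechanism, lower for the premise and the size.

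**What to change.** State in Study Design which VAS reading is screening and which is baseline. If they are separate and the baseline is the later one, nothing more is needed beyond that sentence.

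If they are one reading, base the pre/post efficacy conclusion on total VAS, which the Objectives already list. Report the major-symptom change, and any 30% success rate, beside it as descriptive, with a caveat on regression to the mean. This costs wording only. The downside is that total VAS may be less sensitive if only the worst symptom responds.

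Optionally, for patients not yet treated, choose the major symptom on a short remote VAS on an earlier day and take the baseline from the first-visit VAS before treatment. The day should differ because same-day ratings may share error: if they share half their error variance, half of the expected fall remains. The cost is one questionnaire per consented patient, including those later excluded by skin prick. If 30% to 60% test positive (assumed; no rate is given), that is 33/0.7 ≈ 48 to 33/0.4 ≈ 83 questionnaires to reach 33 eligible patients, and more to allow for dropout, since the plan wants 33 to complete. It cannot be applied to anyone already treated, which is possible: the Publication Plan anticipated recruitment from April 2019 and this version is dated May 2022.

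Neither step controls placebo response or enrolment at a time when symptoms are worse than usual; the report should say so.

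### The protocol text describes no adverse-event enquiry after the first, clinic-given application, so tolerability of the four home applications may be under-recorded

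*Combined protocol and SAP*

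**What the plan says.** **Treatment (Study Procedures).** The regimen is "5 applications each delivering 2 micrograms in each nostril, separated by 1 hour". On the first application: "The first treatment will be administered in the clinic to demonstrate how the spray is done, and to monitor for any side effects". For the rest: "The patient will then be provided with 4 additional prefilled syringes with capsaicin to be administered at home". Patients also receive a document giving the dosing times, "so that they can keep track of how many sprays have been completed".

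**Later contacts (Study Procedures).** At week 4 (plus or minus 1 week) patients rate their nasal symptoms, and "the VAS at 4 weeks post-treatment can be done remotely", by phone, email or post as the patient prefers. Week 12 has the same rating, a repeat capsaicin challenge with optical rhinometry, and a brushing: "A nasal brushing will be obtained to determine local IgE levels".

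**Data collected (Study Procedures).** "Information gathered for the study will include: personal health information, major nasal symptoms, allergy skin test results, mucosal IgE levels, and optical rhinometry".

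**Safety (Data and Safety Monitoring).** Serious events are not expected, but some pain and discomfort are, including from the capsaicin. "The principal investigator will be notified of any adverse events, protocol deviations, and other problems". The principal investigator checks once a month that events and deviations have been reported, and the rhinology team meets monthly on the study's status.

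**Analysis (Statistics).** No adverse-event summary is described.

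**The concern.** The plan has a route for passing adverse events on and a regular check of that route, but it does not describe how an event at home comes to anyone's attention. The sponsor sees reason to watch the first application for side effects and expects discomfort from capsaicin. Yet most applications are taken out of sight, and no described contact then asks how they went.

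What is at stake is the tolerability record, not the efficacy result. The study hopes to refine the treatment algorithm by showing which patients benefit, and readers will want to know how well self-administration was tolerated. If patients are not asked, a low count cannot be told apart from low ascertainment, and analysis cannot recover the difference. If a patient stops home dosing because of discomfort, none of the data items named would show the reason.

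**Working it through.** The plan gives no safety figure to reproduce. The check is a reading of each step for an adverse-event enquiry, followed by a count of applications and an illustration.

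**1. Step by step (Study Procedures; Data and Safety Monitoring)**

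| Step | Described content | Adverse-event enquiry described? |
|---|---|---|
| Application 1, clinic | Demonstration and side-effect monitoring | Yes, by observation |
| Applications 2 to 5, home | Log of times and sprays; its return is not mentioned | No |
| Week 4 | Symptom rating, possibly remote | No |
| Week 12 | Symptom rating, brushing, capsaicin challenge with rhinometry | No |
| Data list | Five items | Not named |
| Safety section | Notification and monthly check | Route only; no question, form or time window |

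The symptom scale covers rhinorrhea, obstruction, itching and sneezing. It could show lasting worsening of these, but it has no item for pain or other discomfort. Its next scheduled use after the home applications is at week 4, that is 3 to 5 weeks after treatment.

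**2. Count of treatment applications**

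Inputs: 5 applications per patient and 1 in clinic (Study Procedures); 33 planned completers (Statistics).

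- Total: 33 × 5 = 165
- In clinic: 33 × 1 = 33 (20%)
- At home: 33 × 4 = 132 (80%)

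**3. Illustration: what a zero count would mean**

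Let *s* be the share of affected patients whose event is recorded. The documents give no value, so 1, 0.5 and 0.25 are assumptions. With no affected patient recorded among *n* = 33, the one-sided 95% upper bound on the recorded rate is 1 − 0.05^(1/33) = 0.0868. Dividing by *s* gives the bound on the true rate:

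- *s* = 1: 8.7%
- *s* = 0.5: 0.0868 / 0.5 = 17.4%
- *s* = 0.25: 0.0868 / 0.25 = 34.7%

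The other way round, for a harm that truly affects 10% of patients (also an assumption), the chance of recording at least one case is 1 − (1 − 0.10*s*)^33:

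- *s* = 1: 1 − 0.900^33 = 96.9%
- *s* = 0.5: 1 − 0.950^33 = 81.6%
- *s* = 0.25: 1 − 0.975^33 = 56.6%

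**Limits of the illustration.** It suits only a kind of event that the protocol does not already expect, since some discomfort is foreseen and a zero count there is implausible. A reduced *s* applies to harms from home applications, because the first is observed. The 33 are completers; the number who receive any dose may be larger.

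**The case against.** The strongest reply is that the point argues from silence. The protocol lists a Study Schedule and a Consent Document as attachments, and neither is in the text reviewed. Either could hold an adverse-event question or reporting instructions. This stands: a reader might infer that patients are never asked about side effects, or that harms are recorded only if volunteered, and the documents do not establish either.

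Other parts of the reply also have weight:

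- **Contacts.** Week 4 may be a phone call, the protocol mentions physician visits, and week 12 is in person. Staff may well ask. But asking is not described, and a posted or emailed scale need involve no conversation.
- **Observed exposure.** Patients also undergo capsaicin challenges with rhinometry at the first visit and at week 12, so the first application is not the only exposure during study procedures. The challenge dose is not given, so these cannot be equated with treatment applications, and they say nothing about the home ones.
- **The data list.** It is worded as what data will include, so it need not be exhaustive. Absence from it is supporting evidence, not proof that events go unrecorded.
- **Oversight.** The investigator must be told of any event or deviation, and the monthly review is a real safeguard. Nothing limits it to volunteered events, but it is described as checking that events were reported, not as seeking them from patients.
- **Consequence.** No objective concerns safety and no safety claim is planned. Calling a future report of few events an artefact would go beyond the documents, as would saying that reasons for stopping are lost: sprays are logged and deviations notified.

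What survives is narrower: the text sets out procedures contact by contact, and none after the first application includes an adverse-event enquiry.

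**Conclusion.** The point holds as a gap in the described data collection. Four of five applications (132 of 165 in 33 completers) are taken at home, and the text describes no later step that would elicit adverse events from them. Notification and monthly review handle events that become known. Tolerability of the home applications may therefore be under-recorded.

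The size of any under-recording cannot be derived from the documents. The range from 8.7% through about 17% to about 35% shows how much a zero count depends on capture; it does not estimate capture in this study. The gap itself does not depend on those figures.

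The primary efficacy comparisons and the secondary prevalence and IgE objectives are not affected. The change is worth making because it is cheap and because events not asked about cannot be recovered at analysis. The conclusion rests on the text reviewed and would weaken or fall if the attachments already contain a scheduled enquiry.

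**What to change.** First check the Study Schedule and Consent attachments. If they already set out an adverse-event enquiry, bring it into the body of the protocol. If not:

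1. Add a side-effect entry for each application to the existing home log, and state that the log is collected.
2. Ask one fixed adverse-event question with the week-4 rating, worded alike for phone, email and post, and again at the week-12 visit.
3. Name adverse events in the list of information gathered under Study Procedures.
4. Add to Statistics a descriptive summary of adverse events for all patients who received any dose, with that number as the denominator.

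The cost is one column on an existing form, one question at two existing contacts and slightly more data entry. No visits or staff are added. More minor events will probably be recorded, so the report should say that events were solicited.
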